5.7 Imputation of Partial Dates

Appendix 1 details partial date conventions that will be used for the determination of treatment-emergent adverse events, prior and concomitant medications, and procedures / therapies subsequently used after a rescue medication is taken / administered.

End of Study Date

Missing study end dates will not necessarily be imputed at the end of the study. However, in the event of an ongoing reporting need, end of study dates may be imputed as the earliest of the data cutoff date, date of death, or last date recorded on the CRF.

5.8 Multiple Assessments and Visit Windows

Nominal visits (e.g. those identified by the study CRF) will be the basis of summarization and statistical analysis. Unscheduled data may be included in summaries of most extreme and baseline values, summaries of specific abnormalities any time post-baseline, and patient data listings.

Sponsor: SpineThera Australia Pty. Ltd

Protocol Number: CLIN-0012-STA01-19

SAP Version and Date: Amendment Final 1.1, 13JUL2022

5.9 Missing Data

Missing data imputation for the primary efficacy endpoint is described in Section 0; AE and concomitant medication date imputations are described in Section 5.7. Otherwise, missing data will not be imputed.

6 STUDY PATIENT DATA

6.1 Analysis Populations

Intention-to-treat (ITT) Population: Defined as all randomized patients. Patients will be included in the treatment group to which they were randomized, regardless of treatment received.

Safety Population (SAF): Defined as all randomized patients who proceed to TF-EI (includes patients with attempted but halted or failed TF-EI). Patients will be included in the treatment group based on the treatment that was received. All safety analyses will be conducted in the Safety Population.

Modified Intention-to-treat (mITT) Population: Defined as all randomized treated patients who receive IMP or placebo by TF-EI. Patients will be reported based on randomized treatment assignment. All efficacy analyses will be conducted in the mITT Population.

Per-protocol Population (PP): Defined as all randomized patients who met all inclusion/exclusion criteria, did not have any significant protocol deviations, complied with the assigned study treatment, returned to the study site for the Primary Efficacy visit within the specified window, or discontinued study early due to lack of treatment effect or received therapy other than study specified drug during the study. Patients will be reported based on actual treatment received. The primary endpoint efficacy analysis will be repeated in the PP population. In order to minimize bias, the PP population will be defined prior to unblinding.

PK population: Defined as all patients who received IMP or placebo and with intensive blood collections in the first 24 hours (approximately 60 subjects). All PK analyses will be conducted in the PK population.

6.2 Patient Disposition

Summaries of analysis population membership and final patient status (completed or withdrawn), including reasons for withdrawal, will be produced based on all patients enrolled. Data will be presented by treatment group as well as overall for the study.

Randomization details, analysis populations, and final patient disposition status will be listed.

6.3 Protocol Deviations

Protocol deviations will be identified and classified as major or minor (violations) before the database is locked. Protocol deviations may include but are not limited to:

- Visit / Procedure / Assessment outside protocol window
- Visit / Procedure / Assessment not done
- Inclusion / Exclusion

Sponsor: SpineThera Australia Pty. Ltd

Protocol Number: CLIN-0012-STA01-19

SAP Version and Date: Amendment Final 1.1, 13JUL2022

- Informed Consent
- Study drug administration
- Study restrictions
- Other

Protocol deviations will be summarized by treatment group and overall for the study.

A listing of protocol deviations will be provided.

6.4 Demographic and Baseline Characteristics

Patient demographics will be summarized and listed for the ITT Population. These will include age, sex (Male / Female), ethnicity (Hispanic or Latino / Not Hispanic or Latino / Not reported / Unknown), race (Black or African American / American Indian or Alaska Native / Asian / Native Hawaiian or Pacific Islander / White / Other / Not reported), baseline height (cm), baseline weight (kg), and BMI (kg/m²). Years since radicular pain associated with lumbar intervertebral disc herniation will be calculated from the start date of pain as reported on the eCRF to the date of screening and will be summarized using descriptive statistics. Leg raise (degree) assessments at Screening will be included as baseline characteristics and will be summarized. Data will be presented by treatment group as well as overall for the study.

The following conversions and equations will be used as applicable:

Height (in cm) = height (in inches) * 2.54

Weight (in kg) = weight (in lbs) * 0.4536

BMI (kg/m²) = weight(kg)/[height(m)²]

6.5 Medical History

Medical History will be coded based on the Medical Dictionary for Regulatory Affairs (MedDRA) for reporting by system organ class (SOC) and preferred term (PT) and will be summarized in descending order of overall incidence. A listing of medical history will be provided for all patients in the ITT population.

6.6 Prior and Concomitant Medication

The incidence of medication use will be summarized by WHO Drug Dictionary anatomic therapeutic class (ATC) Level 2 classification (i.e., therapeutic main group) and preferred name. A patient will be counted only once at each level of reporting. Prior medications are those which have been identified to have been discontinued prior to the treatment date (e.g., taken exclusively during the pre-therapy period). Concomitant medications are those which have been identified to have been taken at any point during the on-therapy period. This includes rescue therapies. Prior and concomitant medication use will be summarized separately and presented by treatment group.

All prior and concomitant medication data will be listed for patients in the ITT population and will include the verbatim and preferred drug name and ATC Level 2.

Sponsor: SpineThera Australia Pty. Ltd

Protocol Number: CLIN-0012-STA01-19

SAP Version and Date: Amendment Final 1.1, 13JUL2022

6.7 Concomitant Procedure / Therapy

The incidence of concomitant procedure / therapy will be summarized. A patient will be counted only once per procedure / therapy. Concomitant procedures / therapies are those which have been identified to have been taken at any point during the on-therapy period. Prior and concomitant medication use will be summarized and presented by treatment group.

All concomitant procedure / therapy data will be listed for patients in the ITT population. A listing for recovery procedures post TF-EI will be produced for the ITT population.

6.8 Study Drug Exposure and Compliance

The number and percentage of patients who attempted, halted, or failed the TF-EI procedure will be summarized in the ITT Population. For patients who complete the TF-EI procedure, the number and percentage receiving IMP per the delivery protocol will also be tabulated. The number and percentage of mis-dosed patients will also be summarized.

Listings of planned and actual treatments, and compliance with TF-EI procedure and delivery protocols of drug administration will be produced for the ITT population.

7 EFFICACY

All efficacy analysis reporting will be based on the mITT Population. Additionally, the primary efficacy analysis will be repeated in the PP Population.

7.1 Primary Efficacy Endpoint and Analyses

Efficacy assessments will be based on the categorical measure of 50% Responder, defined as a patient with 50% or greater improvement in mean Worst Daily Leg Pain (WDLP) score compared to baseline. The mean WDLP score will be derived from the E-Diary recordings entered by the subjects, [REDACTED]

[REDACTED]

[REDACTED]

[REDACTED]

[REDACTED]

[REDACTED]

[REDACTED]

Incomplete Mean Worst Daily Leg Pain score:

All subjects with 5 or more Worst Daily Leg Pain scores recorded in the 10 days preceding the study visit will be included in the analysis. If a subject has less than 5 scores preceding a visit, the subject will not be included in the efficacy assessment for that particular visit. If that same subject has provided 5 or more scores in the 10 days preceding a later visit, the subject will be included in the efficacy assessment for the later visit.

Early Withdrawal:

If a subject withdraws from the study before their 180 day visit, the subject will be included in analyses up to the time that they either stop attending follow-up visits or their consent was withdrawn.

Rescue Medication:

If a patient has failed rescue medication (defined as taking rescue medication for >14 days, taking rescue medication in more than one episode, or receiving treatment beyond the rescue medication regimen defined in the protocol

then the patient will be deemed a non-responder at all timepoints after exceeding the allowed rescue medication, on the day the second episode of Rescue Medication began, or after receiving the additional treatment. The patient will be included in all subsequent timepoints as a non-responder, whether withdrawn or not.

7.1.1 Mean Worst Daily Leg Pain Score: Proportion of Patients with 50% or Greater Improvement from baseline at 60 Days Post-Dosing (Primary Endpoint)

The number and percentage of patients experiencing a 50% or greater improvement from baseline in mean Worst Daily Leg Pain score (i.e. the number and percentage of 50% Responders) will be tabulated for each treatment group. The primary analysis will descriptively compare the proportions of 50% Responders in each of the three arms. The “study success” criterion is defined as the observed percentage of 50% Responders in the high dose group being at least 10 percentage points greater than the corresponding rate in the placebo group.

Listings of Worst Daily Leg Pain will be provided for the modified intent-to-treat population.

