	
Safety population: All subjects randomized who proceed to TF-EI (includes patients with attempted but halted or failed TF-EI). In the Safety population, subjects will be included in the treatment group based on the treatment that was received.
 
Modified Intent to Treat (mITT) population: all randomized subjects who receive IMP or placebo by TF-EI.
 
Per Protocol population: all randomized subjects who complete the study without any major protocol violations.
 
PK population: All subjects who received IMP or placebo and with intensive blood collections in the first 24 hours.

Rescue Therapies available:	
Any one of the Group 1 and/or any one of the Group 2 rescue medications are available for increases in pain for selection and prescription by the Investigator for up to 14 days (once during the study) as addition to the medications currently used by the patient, with special consideration of safety and potential drug interactions.
 
Group 1 (one of):
 
Amitriptyline 5 – 50mg Nocte, or
 
Pregabalin 25mg – 300mg BD, or
 
Gabapentin 100mg TDS dosage, up to 600mg TDS
 
(Acute withdrawal of gabapentin or pregabalin can result in withdrawal symptoms, with likelihood related to dose and duration of treatment. If appropriate, down-titration should take place over at least a week, starting no later than day 15 after rescue began.)
 
and/or Group 2 (one of):
 
Tramadol 100mg – 200mg BD, or
 
Tapentadol 50 – 200mg BD
 
[REDACTED]
 
[REDACTED]
 
[REDACTED]

CLINICAL PROTOCOL

Sponsor: SpineThera Australia Pty Ltd

CLIN-0012-STA01-19 Revision: 06
Effective Date: 17 Jun2020

Page: 11 of 76

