23 ASSESSMENTS

23.1 Efficacy Assessments.

Efficacy assessment will be based on the categorical measure of a Responder, defined as the proportion of subjects at Day 60 post-dosing in each active dose group compared to placebo with a 50% or greater improvement in Mean Worst Daily Leg Pain (WDLP) score compared to baseline. This pain scoring data will be derived from the E-Diary recordings entered by the subjects using eREsearch Technologies Inc electronic Clinical Outcome Assessment SALIENT Clinical Study app (ERT LPRI 424/301). WDLP score will be collected via the app once daily between 18:00:00 and 23:59:59 using the prompt *What was your worst leg pain today?* and a visual scoring range of 0 (no leg pain) to 10 (worst imaginable leg pain).

Subjects will be trained and reminded at each study visit to enter a measure of worst daily leg pain in the evening of each day. This is to establish a learned behaviour that ensures appropriate recording of the essential time period from which the mean values are derived. Where WDLP score has not been entered into the SALIENT Clinical Study app for a given 24hour period, an email notification will be automatically sent to the study team to follow up with the subject to ensure ongoing compliance to submission of WDLP data. The mean WDLP will be calculated as defined further below.

It is important that the critical levels of Mean Worst Daily Leg Pain (NRS Score of 5.0-9.0) is *NOT communicated to the patient at any stage* so that they remain unprogrammed and objective in any daily scoring.

The information contained in this document is the property of SpineThera Australia Pty Ltd and may not be reproduced, published or disclosed to others without written authorization.

CLINICAL PROTOCOL

Sponsor: SpineThera Australia Pty Ltd

CLIN-0012-STA01-19 Revision: 06
Effective Date: 17 Jun2020

Page: 55 of 76

If, in the opinion of the Investigator, additional treatment beyond the rescue medication approach provided in this protocol is required, for example surgery, the patient will be deemed a non-responder in the efficacy analysis at timepoints after the additional treatment but will continued to be followed in the safety population. In this case, the patient shall not continue to report worst daily leg pain score in the electronic diary but shall continue to record concomitant therapy and safety measures in the paper diary.

[REDACTED]

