23.5.4 Vital Signs

Blood pressure and pulse rate will be recorded at study visits and will be taken preferably using an automated recording machine programmed to take preferably 3 consecutive readings at least 2 minutes apart, with the subject seated comfortably for at least 3 minutes prior to blood pressure readings. Respiratory rate and temperature will be measured at all study visits.

23.5.5 Concomitant Medications/Therapies.

CLINICAL PROTOCOL

Sponsor: SpineThera Australia Pty Ltd

CLIN-0012-STA01-19 Revision: 06
Effective Date: 17 Jun2020

Page: 58 of 76

All concomitant medications and therapies in the preceding 30 days will be recorded at the Screening Visit and any changes or additions to medications or therapies for any medical reason or additions of rescue medications as listed in Section 25.8.1 must be recorded at each subsequent study visit.

The pain-relief needs of the subject should be carefully assessed at each study visit following IMP/placebo administration and prescribed medications and therapies tailored to the needs of the subject.

If, in spite of continued therapies, the subject requires additional analgesic medication for radicular pain, then a choice of rescue medication as listed in Section 25.8.1 can be added as deemed necessary and safe by the Investigator. If, in the opinion of the Investigator, additional treatment for radicular pain beyond the rescue medication provided in this protocol is required, the patient will be deemed a non-responder in the efficacy analysis at timepoints after the additional treatment but will continued to be followed in the safety population.

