25.8 Treatment of Subjects

25.8.1 Rescue Medication

All subjects entering this study are required to keep all analgesic medication and other therapy usage [such as physiotherapy, acupuncture, or TENS] stable or decreased during the study, and only use the rescue pain medication as needed and specified by the protocol.

If pain control is unsatisfactory, the Investigator has a range of Rescue medications that can be added to the maintenance therapy that the subject takes as concomitant medications.

Any one of the Group 1 and/or any one of the Group 2 rescue medications are available for increases in pain for selection and prescription by the Investigator for up to 14 days (once during the study) as addition

The information contained in this document is the property of SpineThera Australia Pty Ltd and may not be reproduced, published or disclosed to others without written authorization.

CLINICAL PROTOCOL

Sponsor: SpineThera Australia Pty Ltd

CLIN-0012-STA01-19 Revision: 06
Effective Date: 17 Jun2020

Page: 64 of 76

to the medications currently used by the patient, with special consideration of safety and potential drug interactions.

Group 1 (one of):

- Amitriptyline 5 – 50mg Nocte, *or*
- Pregabalin 25mg – 300mg BD, *or*
- Gabapentin 100mg TDS dosage, up to 600mg TDS

(Acute withdrawal of gabapentin or pregabalin can result in withdrawal symptoms, with likelihood of withdrawal related to dose and duration of treatment. If appropriate, down-titration should take place over at least one week, starting no later than day 15 after rescue began.)

and/or Group 2 (one of):

- Tramadol 100mg – 200mg BD, *or*
- Tapentadol 50 – 200mg BD

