4.3 Multiple Comparisons and Multiplicity

No formal statistical hypothesis tests will be conducted.

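### SAP 7.1 counts more than 14 days of rescue as failure, with no visible exception for the gabapentin or pregabalin taper in Protocol 25.8.1: a minor point to confirm or fix

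*SAP*

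**What the plan says.** **Protocol.** Section 25.8.1 permits one rescue episode of up to 14 days: one Group 1 drug (amitriptyline, pregabalin or gabapentin), one Group 2 drug (tramadol or tapentadol), or both. Because stopping gabapentin or pregabalin abruptly can cause withdrawal symptoms, it adds: "If appropriate, down-titration should take place over at least one week, starting no later than day 15 after rescue began". The Synopsis gives the same instruction.

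The visible non-responder rule has no day count. Section 23.1 applies it when "additional treatment beyond the rescue medication approach provided in this protocol is required, for example surgery, the patient will be deemed a non-responder", and section 23.5.5 when "additional treatment for radicular pain beyond the rescue medication provided in this protocol is required, the patient will be deemed a non-responder".

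**SAP.** The Rescue Medication paragraph of section 7.1 defines failed rescue by three limbs. The first is duration: "If a patient has failed rescue medication (defined as taking rescue medication for >14 days". The others are a second episode of rescue, and treatment beyond the protocol's regimen. The consequence is stated as "then the patient will be deemed a non-responder at all timepoints after exceeding the allowed rescue medication", and it persists: "The patient will be included in all subsequent timepoints as a non-responder, whether withdrawn or not".

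The Day 60 responder count feeds the success criterion in SAP 7.1.1: the observed high-dose responder percentage must be at least 10 points above placebo. Otherwise the analysis is descriptive; SAP 4.3 says "No formal statistical hypothesis tests will be conducted".

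**The concern.** The protocol places the taper inside its rescue approach, and a taper that starts on day 15 lies wholly after the 14 days. The protocol therefore foresees a compliant patient taking the drug for more than 14 days. The SAP lists duration as a limb separate from treatment beyond the protocol's regimen, so the duration limb can catch someone who never left that regimen.

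If the rule is programmed from start and stop dates, such a patient becomes a non-responder at all later visits because of a step meant to prevent withdrawal symptoms. A programmer who instead reads the taper as part of the allowed rescue would score the same patient from the diary. The primary endpoint should not depend on which reading is chosen.

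**Working it through.** **The plan's own figures.** The plan gives no figure on this point. Its only computed figures are the power statements for 60 per arm. The pooled-variance normal approximation reproduces them:

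- 50% vs 20%: pooled SE = √(2 × 0.35 × 0.65 / 60) = 0.0871; SE under the alternative = √((0.25 + 0.16) / 60) = 0.0827; (0.30 − 1.96 × 0.0871) / 0.0827 = 1.56, so power is 0.941 (stated 94%).
- 50% vs 25%: (0.25 − 1.96 × 0.0884) / 0.0854 = 0.90, so power is 0.816 (stated 81%).

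The point does not depend on these powers. Only the assumed response rates are reused below.

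**Days on drug.** Take rescue day 1 as the first dose and read day 15 as rescue day 15. A taper of L days starting on rescue day k ends on day k + L − 1.

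| Taper length | Start day | Last day on drug | Over 14? |
|---|---|---|---|
| 7 (protocol minimum) | 8 | 14 | no |
| 7 | 9 | 15 | yes |
| 7 | 15 (latest permitted) | 21 | yes |
| 14 | 15 | 28 | yes |

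A minimum-length taper avoids the duration limb only if it starts by rescue day 8. Starts on days 9 to 15 give 15 to 21 days.

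**Reach to Day 60.** If rescue starts on study day s, the 15th rescue day is s + 14. It falls before a Day 60 visit if s ≤ 45 (42 for a visit on Day 57, 48 for Day 63, the ±3-day window).

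**Overlap with the diary window.** Scores come from the 10 days before the visit, here Days 50 to 59. A taper from rescue day 15 ends on study day s + 13 + L. It is over by Day 49 if s ≤ 29 (L = 7) or s ≤ 22 (L = 14). So with a 7-day taper and rescue begun by Day 29, the literal rule gives a Day 60 non-response although no taper day falls in the window.

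**Sensitivity of the success rule.** SAP 3.3 gives 55 randomized patients; arm sizes are not given, so I assume 18 in each of the two arms compared. One patient is 100 / 18 = 5.6 points. The rule needs k / 18 ≥ 0.10, so k ≥ 1.8: an excess of two responders. Exact binomial chance of meeting it when a given number of diary responders are reclassified:

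| Reclassified | 50% vs 20% | 50% vs 25% |
|---|---|---|
| none | 0.923 | 0.857 |
| 1 in high dose only | 0.857 | 0.764 |
| 2 in high dose only | 0.760 | 0.643 |
| 1 in placebo only | 0.963 | 0.922 |
| 2 in placebo only | 0.984 | 0.961 |
| equal numbers (1 or 2) in both | 0.923 | 0.857 |

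Splits of 19 vs 18 and 18 vs 19 (high dose vs placebo) start from 0.890 and 0.910 under 50% vs 20% and move the same way. The counts of one and two are illustrations; nothing in the documents shows that any such patient exists.

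**The case against.** **Redaction.** This is the strongest objection. The parenthesis that opens the SAP definition never closes in the visible text. SAP 1.0, reproduced after the current version, marks redactions directly before the sentence, inside the definition and after the consequence. Protocol 23.1 and the Synopsis rescue entry are also followed by redacted text, and SAP 7.3 (Sensitivity Analysis) has a heading with no visible content. A taper exemption, or a sensitivity analysis of rescue handling, could sit in any of these places. This stands, and it makes the fix conditional.

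**The allowed rescue medication.** The consequence applies after the allowance is exceeded, and Protocol 25.8.1 sets that allowance with the taper in it. On that reading the two documents agree. This also stands as a possible reading, but the explicit day limit earlier in the same sentence points the other way, so the text needs settling.

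**Counting taper days is defensible.** A tapering patient is still on an added analgesic. This carries less weight: on the visible text, up to 14 days of full-dose rescue may already overlap the diary window without penalty. It is hard to penalise the lower-dose step that the protocol itself prescribes.

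**Rarity.** For a Day 60 score to change, the patient must use rescue, receive gabapentin or pregabalin, be judged to need a taper, start a 7-day taper after rescue day 8, begin rescue by about Day 45, and still show a 50% diary response. No rate is given for any step. This stands and limits the weight.

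A reader might infer that the SAP flatly contradicts the protocol, or that the rule biases the result against SX600. The documents support neither: the wording and redactions leave room for agreement, and affected patients could be in any arm.

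**Conclusion.** On the visible text, a patient who follows Protocol 25.8.1 exactly can be scored a non-responder under SAP 7.1 solely because of the taper. That is a gap in the definition and can reach the primary endpoint.

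The point is minor. The number of patients affected is unknown and may be zero. The direction of any bias is unknown, and equal numbers in both arms leave the chance of meeting the success rule about unchanged. There are no hypothesis tests, and SAP 6.6 lists concomitant medication, including rescue, by patient, so affected cases could be found, though a listing does not settle how they are scored.

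The conclusion assumes that no redacted text exempts the taper and that day 15 means rescue day 15. The size figures also assume 18 per arm and the plan's response rates.

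**What to change.** Unless redacted text already does so, before unblinding (and so before the topline analysis in SAP 3.6 uses treatment assignments):

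1. State in SAP 7.1 that gabapentin or pregabalin down-titration days permitted by Protocol 25.8.1, started no later than day 15 after rescue began, do not count toward the 14 days. The protocol sets a minimum taper length but no maximum; if a maximum is wanted, the sponsor's clinicians should set it blind, and days beyond it would count.
2. Flag taper days in the medication listing, including those that overlap a 10-day diary window.
3. Use the same definition of rescue failure in SAP 7.2.7. A taper alone creates no event date there; the definition matters only when further therapy starts after rescue has been called a failure.

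The cost is one sentence, a flag, and a blinded review of medication records to identify taper days. The downside is that some Day 60 scores would be recorded on a tapering drug: for a taper started on rescue day 15, when rescue began after about Day 29 (7-day taper) or Day 22 (14-day taper). The overlap flag makes those scores visible.

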31.6 Efficacy Analyses

31.6.1 Primary Efficacy Analysis

The primary efficacy endpoint is the proportion of subjects with a 50% or greater improvement from baseline in Mean Worst Daily Leg Pain at 60 days. The primary endpoint will be analysed using a logistic regression model with treatment group (three levels) as a factor. The primary analysis will compare the high dose group to the placebo group using a two-sided test at the $\alpha=0.05$ level of significance. The odds ratio of the high dose group to the placebo group with a 95% Wald confidence interval will also be reported.

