3.2 Randomization and Blinding

Following the original plan in the protocol, patients who are eligible for enrollment into the study will be evaluated for randomization eligibility at Study Visits 1 and 2. The Biostatistician will prepare the randomization schedule, which will be managed by PCI Melbourne. Patients will be randomly assigned in a 1:1:1 ratio to one of two doses of SX600 (12.5 mg for the low-dose group, or 25.0 mg for the high dose group,) or Placebo (0.9% Sodium Chloride for Injection, BP or equivalent), with a planned final assignment of 60 patients/group. The list of randomized treatment assignments will be prepared by statisticians assigned to the study. The randomization number will be collected in the Electronic Data Capture (EDC) System. Refer to the Randomization Materials Specification Form for further details of randomization.

At the site, the physician who performs the TF-EI will be unblinded to the treatment assignment, but a second physician and study staff who are responsible for all subsequent patient assessments

Sponsor: SpineThera Australia Pty. Ltd

Protocol Number: CLIN-0012-STA01-19

SAP Version and Date: Amendment Final 1.1, 13JUL2022

must remain blinded to the treatment assignment. Since the reconstituted active IMP produces an opaque white suspension, it is not possible to blind the injector with a matching placebo solution for epidural administration, and hence 0.9% Sodium Chloride for Injection, BP has been chosen for the placebo comparator.

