3.3 Sample Size Considerations

Limited data are available in the literature on which to base sample size/power considerations. In the study conducted by Ghahreman (Ghahremen, 2010) ⁽¹⁾, the primary endpoint was the proportion of patients who achieved a 50% or greater reduction from baseline at 30 days. In the steroid arm, the observed response rate was 54%. In the control arms of this study, the response rates were 7%, 13%, 19%, and 21%. Based on these results, the assumed true response rates are 50% (active) and 20% (placebo). Using a two-sided comparison of binomial proportions at the alpha=0.05 level of significance, a sample size of 60 patients per arm will provide 94% power. If the true active arm response rate is 50% and the true placebo response rate is 25%, then the power of the study is decreased to 81%.

Due to enrollment difficulties and the impact of Covid-19, the study is being terminated with a total sample size of 55 randomized patients. As a result, the originally planned efficacy analyses will not be conducted. Instead, the results of the study will be evaluated descriptively.

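### SAP 7.1.1 declares success on a 10-point lead in observed responder rate; with about 18 patients per arm, an inert high dose would pass roughly one time in four

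*SAP*

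**What the plan says.** Protocol 31.6.1 planned an inferential primary analysis: "The primary analysis will compare the high dose group to the placebo group using a two-sided test" at the 0.05 level, from a logistic model, with a 95% Wald interval for the odds ratio.

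SAP 3.3 withdraws that plan because "the study is being terminated with a total sample size of 55 randomized patients". SAP 4.3 adds: "No formal statistical hypothesis tests will be conducted". For the primary endpoint, SAP 7.1.1 states: "The primary analysis will descriptively compare the proportions of 50% Responders in each of the three arms".

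The same section then sets a success criterion: the "observed percentage of 50% Responders in the high dose group being at least 10 percentage points greater than the corresponding rate" on placebo. The visible text gives no reason for choosing 10 points and no chance of meeting the criterion when there is no effect. It names no interval for the responder rates or their difference. The only 95% interval visible in the SAP is for the median time to loss of response (7.2.7).

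SAP Section 10, which lists changes to the planned analysis, mentions the move to descriptive analyses and the added topline. It does not mention the criterion.

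**The concern.** An analysis cannot be purely descriptive and also return a verdict. Once a threshold decides whether the study succeeded, there is a decision rule, and its error rates matter whether or not it is called a test. This rule ignores sampling error, which is large with arms of about 18.

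Success is the only verdict that the SAP attaches to the primary endpoint. Under SAP 3.6 the Day 60 result is also read out in a topline before full database lock. If an ineffective dose passes often, a report of success tells the reader little, yet it will be read as evidence that the drug works.

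**Working it through.** **Inputs**
- Threshold: observed high dose minus placebo of at least 10 points (SAP 7.1.1).
- Size: 55 patients (SAP 3.3). Allocation: "Patients will be randomly assigned in a 1:1:1 ratio to one of two doses of SX600" or placebo (SAP 3.2). So 55/3 = 18.3 per arm; actual arm sizes are not stated.
- Response rates: 50% active and 20% placebo, with 25% placebo as the alternative (SAP 3.3). The cited study's control arms had 7%, 13%, 19% and 21%.

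**The plan's own power figures.** Power = Φ{[d - 1.96·√(2p̄q̄/n)] / √[(p1q1 + p2q2)/n]}, with n = 60:
- 50% v 20%: (0.300 - 0.1707)/0.0827 = 1.56, giving 94.1% (stated 94%).
- 50% v 25%: (0.250 - 0.1732)/0.0854 = 0.90, giving 81.6% (stated 81%).

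The design figures reproduce, so the assumed rates are a fair basis for the next step.

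**What passes.** At 18 v 18, one extra responder is 1/18 = 5.6 points (fail) and two are 2/18 = 11.1 points (pass).

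**Chance of passing with no effect.** Give both arms the same true rate p and sum over all outcomes:

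P(success) = Σx Σy Bin(x; nH, p) · Bin(y; nP, p) · 1{x/nH - y/nP ≥ 0.10}

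| High v placebo | p = 7% | 10% | 13% | 20% | 25% | 50% |
|---|---|---|---|---|---|---|
| 18 v 18 | 0.153 | 0.195 | 0.224 | 0.264 | 0.281 | 0.309 |
| 18 v 19 | 0.146 | 0.184 | 0.209 | 0.241 | 0.252 | 0.256 |
| 19 v 18 | 0.160 | 0.187 | 0.192 | 0.191 | 0.201 | 0.256 |
| 19 v 19 | 0.160 | 0.202 | 0.230 | 0.270 | 0.286 | 0.314 |

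The 19 v 18 row is lower because, once placebo has two or more responders, that split needs a lead of three in most cases. If diary exclusions leave 15 v 15, the values are 0.245 at 20% and 0.262 at 25%.

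**Compared with the protocol's test.** A two-sided 0.05 test allows 0.025 in the favourable direction. At 20-25% the ratio runs from 0.191/0.025 = 7.6 to 0.286/0.025 = 11.4.

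**If the high dose is truly worse** (20% v 25% on placebo), the rule still passes with probability 0.167 (18 v 18), 0.147 (18 v 19) or 0.110 (19 v 18).

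**If the design effect is real** (50% v 20%), it passes with probability 0.92, 0.91 or 0.89 for the same splits.

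**What a bare pass looks like.** Take 6/18 v 4/18, a difference of 0.111. The Wilson limits are 0.163 to 0.563 and 0.090 to 0.452. Newcombe's method gives:
- lower: 0.111 - √[(0.333 - 0.163)² + (0.452 - 0.222)²] = -0.175
- upper: 0.111 + √[(0.563 - 0.333)² + (0.222 - 0.090)²] = +0.376

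With placebo at 4/18, the first high-dose count whose lower limit exceeds zero is 10/18 (interval 1.6 to 57.2 points), a 33-point lead.

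**The case against.** The strongest reply is that the SAP has given up confirmatory claims. It says the results are descriptive, attaches no dosing, stopping or development decision to the word success, and tabulates counts from which any reader can compute an interval. On this view, setting the rule against the 2.5% tail of a test designed for 60 per arm compares unlike things. A lenient threshold that passes about 90% of the time at the design effect could also be a sensible screen in a truncated Phase I/II study.

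Part of this stands. The SAP claims no error control, and the rule is sensitive to a large effect. But the documents do not present it as a lenient screen, and its sensitivity does not help a reader who sees only that the study succeeded.

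Four limits also stand:
- One in four is not a fixed figure. It is nearer one in five at 19 v 18, and about 0.15 to 0.16 if the common rate is 7%. Even that is about six times 0.025.
- Parts of SAP 7.1 and the body of 7.3 are not visible, and the table shells are a separate document, so an interval may be specified there. That would not alter the criterion, which uses the point estimate alone.
- The 33-point lead applies to placebo at 4/18. It is smaller when placebo has fewer responders: 22 points at 0/18.
- Section 10 does disclose the move to descriptive analysis; only the criterion is missing from it.

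**Conclusion.** The concern holds. SAP 7.1.1 puts a success label on an observed difference that an inert high dose would reach 26% to 28% of the time at 18 v 18 and the plan's own placebo rates, and 19% to 29% of the time over near-equal splits. That is roughly eight to eleven times the favourable-direction error of the protocol's test. A result that just passes is compatible with the high dose being substantially worse than placebo.

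These figures assume near-equal arms from 55 patients, independent binomial responses and a common true rate of 20% to 25%. Lower common rates reduce the chance of a false pass without making it small. Because the rule governs the headline on the primary endpoint, it should be changed before results are reported.

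**What to change.** In SAP 7.1.1:
1. Report the high-dose-minus-placebo and low-dose-minus-placebo differences in Day 60 responder rate, each with a two-sided 95% interval (Newcombe or Miettinen-Nurminen).
2. Remove the success label. Alternatively, keep 10 points only as a descriptive reference, state beside it the chance of meeting it with no effect (about 0.2 to 0.3 at the plan's rates, recalculated for the actual arm sizes), and say that meeting it is not evidence of efficacy.

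In SAP Section 10, list the criterion as a change from the protocol.

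The cost is a few sentences of SAP text and one extra column in one table; no new data are needed. The drawback is a weaker headline, because the interval will be wide: at 30% v 20%, its half-width is about 1.96·√[(0.3·0.7 + 0.2·0.8)/18] = 28 points. That width is what the trial can support.
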